NCT#: 04228445

To: PVP-19IC01 Principal Investigators

From: Provepharm PVP-19IC01 Study Team

**RE: Removal of Pharmacokinetic sub study from protocol PVP-19IC01 amendment #2:
An Open-Label, Randomized, Multicenter Study to Evaluate the Safety, Efficacy,
Pharmacokinetics and Physician Satisfaction of Two Different Doses of 3,3'-Dioxo-2,2'-
bisindolylidene-5,5'-disulfonate disodium 0.8% Solution When Used as an Aid in the
Determination of Ureteral Patency.**

This Clarification Letter is to remove the pharmacokinetic (PK) sub-study from the PVP-19IC01 protocol, Amendment # 2 dated 02 September 2020.

This protocol specifies that PK samples of plasma, urine and stool will be collected from a subset of approximately 16 subjects from 2 participating PK sites.

Zero patients have been enrolled into the PK sub study due to the difficulty in recruiting patients for the clinical trial during the COVID-19 emergency. Additionally, the logistical complexity involved with conducting the PK portion has made it challenging for the 2 sites to recruit consenting subjects. Therefore, the recruitment of patients for the PK sub study of the trial will be discontinued. A separate PK study will be conducted to obtain the necessary PK data.

Additionally, it was noted that the header of the approved protocol amendment 2, starting at page 19 through the end of the protocol, references the year 2019. The correct year should be 2020.

Please sign and date in the acknowledgment section below, return a copy of the signed document to Provepharm, Inc. and file the original in the current protocol section of your investigational site file.

Approvals:

Sponsor

[figure not shown]

Director, Clinical Operations

Signature and Date

Medical Monitor

Signature and Date

Acknowledged:

Principal Investigator:

Printed Name

Signature and Date

1. INTRODUCTION AND SCOPE

Protocol PVP-19IC01 is an Open-Label, Phase 3, Randomized, Multicenter Study to Evaluate the Safety, Efficacy, Pharmacokinetics and Physician Satisfaction of two different doses of Indigo Carmine Injection 0.8% solution when used as an aid in the determination of ureteral patency.

This Statistical Analysis Plan (SAP) is intended to provide a more technical and detailed elaboration of the principal statistical features stated in the protocols. The objective of the SAP is to reasonably assure that the statistical methodologies to be used for analysis are complete and accurate.

In the development of this SAP, the following documents were used:

- Protocol PVP-19IC01: Amendment 02, 02 September 2020
- PVP-19IC01 eCRF: Version 31. (draft), 28 August 2020

The principles in the following guidance documents are followed in preparation of this SAP:

- ICH E3 (1995): Structure and Content of Clinical Study Reports
- ICH E6 (1996): Guideline for Good Clinical Practice
- ICH E9 (1998): Statistical Principles for Clinical Trials

In the event that a discrepancy is found between the descriptions in the statistical section of the protocol and this document, the description in this document supersedes the descriptions in the statistical section of the protocol.

2. OVERVIEW OF STUDY OBJECTIVES AND ASSESSMENTS

The primary objective of this study is to determine whether the use of Indigo Carmine 0.8% Injection, USP solution for injection (IC) provides a visualization advantage compared to saline when used as an aid in the determination of ureteral patency. Visualization will be measured by a 5-point conspicuity score as follows:

- 1 = No jet observed
- 2 = Weak jet, little color contrast
- 3 = Color contrast or significant jet flow
- 4 = Strong jet flow with good color contrast
- 5 = Strong jet flow with striking contrast in color

Secondary objectives are to assess:

1. To evaluate the safety profile of IC when used as an aid in the determination of ureteral patency.
2. To determine physicians' overall satisfaction with the IC treatment by assessing the proportion of surgeons who agree using the 5-point Physician Satisfaction Agreement Scale (PSAS) with the statement:

“Compared to the saline treatment, my ability to assess ureter patency was improved after the addition of IC.”

- 1. Strongly Agree
- 2. Agree
- 3. Neither Agree nor Disagree
- 4. Disagree
- 5. Strongly Disagree

A surgeon's evaluation is considered satisfactory if the rating is either a 1 (strongly agree) or 2 (agree).

3. To determine proportion of responders. To determine proportion of subjects meeting the responder definition in conspicuity score following IC treatment based on the blinded central reviewer's assessment. A subject is a responder when there is ≥ 1 point difference in the conspicuity score following the IC vs saline treatment (IC – Saline ≥ 1) and the conspicuity score following the IC treatment is (3, 4, or 5). The responder criteria will be assessed separately for each ureter for each subject.

4. To describe the time to visualization (TTV) of blue color in the ureteral jets flow following IC treatment when used as a visualization aid during urological and gynecological surgical procedures
5. To determine the IC pharmacokinetic profile in a subset of subjects from 2 investigational sites.
6. An exploratory comparison will be done on the difference between the IC high dose vs IC low dose. Surgeons will be blinded to the dose of IC.

The study will enroll approximately 116 subjects from approximately 10 – 20 study centers in the United States. Subjects scheduled for urological or gynecological surgical procedures, age 18 to 85 years inclusive, will be screened for participation. Screening will occur within 30 days before study drug administration (Day of Surgery). After signing the informed consent, medical history, physical examination, baseline laboratory testing, pregnancy testing, 12-lead ECG, and vital sign measurements will be completed during the screening visit. Any procedure done for the purpose of the surgery before the date of signing the informed consent may be used as long as it was within 30 days of the scheduled surgery date.

On the day of surgery (Day 1) the subject will be evaluated for eligibility for randomization. Eligible subjects will be randomized to receive a dose of either IC high dose (5 mL) or IC low dose (2.5 mL). Each randomized subject will serve as his/her own control by receiving a dose of normal saline prior to receiving the randomized IC dose. The surgeon will be blinded to the IC dose a subject receives. Time of injection of saline and IC will be captured.

To evaluate the efficacy outcomes, each subject will first be injected intravenously with 5 mL 0.9% saline. The ureteral orifices/flow will be observed and video recorded for 10 mins. The time period that will be captured on video is from injection to 10 minutes post injection. If both ureters cannot be visualized simultaneously, then alternating 15-30 second images of each ureter or ureteral orifice will be obtained. The process will be repeated in the same patient for the IC dose. Hence, each subject will have 2 videos and each will be about 10 minutes in length.

The videos will be sent to a central imaging group that will pool and blind the videos. Videos will then be assessed by 2 blinded central reviewers for assessment of ureteral patency using the 5-point conspicuity score criteria. The 2 independent central reviewers will provide 2 conspicuity scores (1 for left ureter and 1 for right ureter) for each video. The consistency between the two reviewers will be checked; the two reviewers will be considered consistent if their scores for the corresponding ureter is (+/-) 1 point of a given video. In this case, the average score across the two reviewers will be the final score for efficacy analysis. Otherwise, a third reviewer (a judicator) will step in and will review this video. The scores from this third reviewer will be the final score for this video for efficacy analysis.

After the procedure, the surgeon performing the procedure will provide his/her overall satisfaction assessment by rating his/her agreement with the statement “Compared to the saline

treatment, my ability to assess ureteral patency was improved after the addition of IC” using the PSAS: 1=Strongly Agree, 2=Agree, 3=Neither Agree nor Disagree, 4=Disagree, 5=Strongly Disagree.

In addition, after the procedure the surgeon will also review the videos of his/her patients and will provide the conspicuity scores for each ureter after each treatment using the same 5-point conspicuity score criteria. The surgeons score will be utilized for conspicuity score concordance analysis.

In a subset of subjects from 2 sites (about 16 subjects), subjects will be consented to participate in the pharmacokinetic (PK) portion of the study. Once consented, 13 blood samples will be taken from each subject at the scheduled timepoints post IC treatment for PK analysis. Urine collection will occur by a voided sample within 1 hour prior to the surgery and post IC injection for the following time periods 0-2 hours (including any urine drained during surgery), 2-6 hours, and 6-12 hours. The first post-op stool will also be collected for analysis in this PK group.

All treated subjects will have a follow-up visit 7 to 30 days (\pm 2 days) after the procedure. A final telephone follow-up call will occur on Day 30 (\pm 2 days) in subjects who have the follow-up visit before Day 28.

Safety assessments will include monitoring of AEs during and post the procedure, clinical laboratory tests, 12-Lead ECG, and vital sign measurements.

Protocol Schedule of Assessment is included here for the convenience of review.

Table 1: Schedule of Assessments

	Screening period Day -30 to -1 ¹	Randomization/ Treatment Day 1	Follow-up Visit Day 7 to Day 32 or Early Termination ²	Telephone follow-up if Follow-up visit prior to Day 28
Informed Consent	X			
Inclusion / Exclusion Criteria	X	X		
Medical, surgical history, demography, medication review	X			
Physical Examination	X		X	
Height	X			
Weight	X			
Vital Signs	X	X ³	X	
12 Lead ECG	X		X	
Randomization		X		
Concomitant Medications	X	X	X	X
AE/SAE		X	X	X
Blood Safety Labs ⁴	X		X ⁵	
PK Blood ⁶ , Urine ⁷ , and Stool ⁸ collection		X		
Bowel Prep ⁹ (PK group)	X (Day -1)			
Surgery		X		
Surgeon satisfaction with IC treatment		X		
0.9% saline injection		X		
0.8% IC injection		X		
Video filming of ureteral jet flow with saline and with IC		X		
Surgeon conspicuity score of urine Jet flow		X ¹⁰		
Urine Pregnancy Test ¹¹		X		

1. Bloodwork/ECG completed as part of the pre-operatively work-up (within 30 days of surgery) will be acceptable for study use and will not have to be repeated for study participation.
2. Subjects who have onsite visit between Day 7 and 27 may have safety follow-up completed with an additional telephone call between Day 28-32.
3. Continuous monitoring, including heart rate and rhythm, will be required during the procedure and in the immediate post-operative period, vital signs will be collected for the study at the following specific time points: immediately prior to each injection and 5 minutes after each injection and thereafter approximately every 15 minutes through 1 hour following the procedure
4. Blood Safety Labs: hematology = White blood cell count (WBC), Red blood cell count (RBC), Hemoglobin, Hematocrit, platelets, differential blood count (Neutrophils, lymphocytes, monocytes, eosinophils, basophils). Serum chemistry = total bilirubin, AST, ALT, alkaline phosphatase (ALP), creatinine, blood urea nitrogen, sodium, chloride, potassium, bicarbonate, phosphorus, calcium, glucose, albumin.
5. Must be performed at the same laboratory as the initial bloodwork.
6. For approximately 16 Subjects at 2 planned sites blood plasma collection will occur prior to and post IC injection at 2, 5, 7, 10, 15, 20, 30, and 40 mins, then at 1, 2, 3, 4 hours after IC administration.
7. For approximately 16 Subjects at 2 planned sites urine collection will occur by a voided sample within 1 hour prior to the surgery and post IC injection for the following time periods 0-2 hours (including any urine drained during surgery), 2-6 hours, and 6-12 hours
8. The first post-op stool will be collected and sent for analysis for IC and/or its breakdown products.
9. Bowel prep will be required preoperatively (Day -1) for Subjects in the PK/Breakdown product collection patients.
10. The Surgeon should review the videos post-surgery to perform their conspicuity scoring of the urine jet flows. Scoring should not be done during surgery
11. Urine Pregnancy Tests will be done on day of surgery on all women of childbearing potential.]

2.1. Study Endpoints

2.1.1. Efficacy Endpoints

The **primary** efficacy endpoint is conspicuity score after each treatment provided by the central readers:

- 1 = No jet observed
- 2 = Weak jet, little color contrast
- 3 = Color contrast or significant jet flow
- 4 = Strong jet flow with good color contrast
- 5 = Strong jet flow with striking contrast in color

The **secondary** efficacy endpoints include:

1. Proportion of physicians who agree that compared to saline, IC treatment improves visualization as an aid for the assessment of ureteral patency
2. To determine proportion of IC treatment responders per the blinded central reviewers' assessment. A subject is a responder to the IC treatment when there is ≥ 1 point difference in the conspicuity scores between the IC and saline treatment (IC – Saline ≥ 1) and the conspicuity score following the IC treatment is (3, 4, or 5). The responder criteria will be assessed separately for each ureter for each subject.
3. Time (minutes) from start of drug administration to visualization (TTV) of the blue color in the ureteral jets flow after IC administration

Other efficacy endpoints will include:

1. Conspicuity scores assessed by the surgeons
2. Concordance of the Conspicuity scores between the surgeons' assessments and the blinded central reviewers' assessments.

2.1.2. Safety Endpoints

The safety endpoints include

1. Treatment emergent adverse events

2. Proportion of subjects with clinically important changes in clinical safety laboratory tests after treatment
3. Proportion of subjects with clinically important changes in vital signs after treatment
4. Proportion of subjects with clinically important changes in ECG after treatment

3. GENERAL CONSIDERATIONS

3.1. Sample Size Determination

Indigo carmine (IC) was introduced into clinical practice in 1903 by Voelcker and Joseph and was originally used as a test of renal function (Lacy 1955). In the 100+ years since then, IC has been used as a vital dye during surgery to identify vessels, tissues, and fistulae, and to help visualize ureteral urine ejection jets after urogynecological surgery. All these indications rely on IC's deep blue color to identify tissues and structures. IC is a contrast stain that produces a very vivid coloration and is not absorbed by cells (Jung 1999).

It is therefore expected that IC will be more effective than Saline in providing visualization when used as an aid in the determination of ureteral patency. The total sample size of 116 patients, therefore, was estimated based on empirical assumptions [REDACTED]

Therefore, the total sample size for this study will stay the same (approximately 116 patients) as planned before the protocol amendment.

Table 2:

The image is a high-contrast, black-and-white abstract graphic. It features a grid of horizontal and vertical lines. Several large, solid black rectangular blocks are placed across the grid. In the top left, there is a small black square. In the top center, there are two black rectangles, one above the other. In the top right, there is another black rectangle. In the middle left, there is a large black rectangle. In the middle center, there is a black rectangle with a small white square to its left. In the middle right, there is a black rectangle. In the bottom left, there is a large black rectangle with a small white square to its left. In the bottom center, there is a long, thin black rectangle. In the bottom right, there is a large black rectangle with a small white square to its right. The background is a light yellow color.

estimates.

3.2. Interim Analysis

A formal interim analysis is planned in Protocol Amendment 2. Patient enrollment was paused while the conspicuity score criteria was developed. A total of 21 patients were randomized and treated at the time of enrollment pause. Since the study total sample size of approximately 116 patients to be enrolled will remain unchanged for the protocol amendment, and that the 21 subjects enrolled prior to 5-point conspicuity score is developed will be excluded from the final efficacy analysis (see Section 3.3), the timing of this planned interim analysis will be based on the enrollment of the remaining approximately 95 subjects. That is, this formal interim analysis is to be conducted when approximately 50% of the remaining patients are randomized and treated (approximately 47-48 patients). The objective of this interim analysis is to confirm the observed treatment effect size on the conspicuity score from the test dataset. The interim analysis will only analyze the conspicuity score provided by the central reviewers.

Since randomization to the IC dose level will not be unblinded during the interim analysis, the overall IC treatment effect will be analyzed using the proportional odds model; the model will include the main effect of treatment (IC vs Saline) and ureter (left vs right) and control for the repeated measures within a subject. This model is identical to the reduced model (Model 2) in the primary analysis of the primary endpoint described in **Section 5.1**.

Conditional Power (CP) will be calculated based on estimated odds ratio and corresponding standard error in log scale from the interim analysis data based on equation from Lan and Wittes

(1988) as summarized by professor Gary Kock in 2003 at Drug Information Association (DIA) 10th Annual Biostatistics Workshop in Japan, August 29, 2003 in Tokyo, Japan¹.

The prediction of the conditional power for a statistically significant result from the final analysis (at the two-sided 0.05 level) given the observed difference between treatments at a formal interim analysis can be based on the estimated treatment effect (equation 2); 2-sided 95% confidence intervals for the CP will also be calculated.

2. Estimated conditional power if the observed treatment difference at the interim analysis applies to the remainder of the study

$$\text{ProbNorm} \left\{ \left[\sqrt{\frac{(1-P)}{P}} + \sqrt{\frac{P}{(1-P)}} \right] Z - \frac{Z_\alpha}{\sqrt{1-P}} \right\}$$

where $Z = (\hat{T} / \text{SE})$

3. 100(1- γ) confidence interval for conditional power on the basis of \hat{T} and SE

$$\text{ProbNorm} \left\{ \sqrt{\frac{(1-P)}{P}} \times (Z \pm Z_\gamma) + \sqrt{\frac{P}{(1-P)}} \times Z - \frac{Z_\alpha}{\sqrt{1-P}} \right\}$$

Where T_{hat} = estimate of treatment effect at interim and SE = standard error of the treatment effect. In this study, T_{hat} will be the estimate of odds ratio of treatment and SE will be the standard error of the estimate, both are in the log scale. P =proportion of study completed (=0.5), alpha (α)=0.05/2, gamma (γ)=0.05

Following Mehta et al (2011, page 6)² adaptive approach the interim analysis results will be classified into three zones based on the estimated CP and decision to be made in each zone is specified as follows.

¹ Page 8 “Statistical Considerations for the Conduct and Reporting of Interim Analyses”. (GGK 8/11/2003)

² Adaptive increase in sample size when interim results are promising: A practical guide with examples. Cyrus R. Mehta and Stuart J. Pocock. Statist. Med. 2011, 30 3267--3284

Table 3: Interim Analysis Conditional Power and Decision Principle

Conditional Power	Decision	Rationale
CP <0.20	Stop the study because the evidence for unfavorable efficacy is sufficiently convincing that no additional efficacy data is necessary.	An unfavorable zone: the conditional power (CP) is fairly low, suggesting that the final result is not likely to achieve significance, hence, the study has fairly low probability to reject the null hypothesis. This zone is defined to be CP < 40%
0.2 <=CP <0.4	No sample size re-estimate because the evidence for unfavorable efficacy. Complete the study per current protocol.	
0.4 <=CP <=0.8	Re-estimate sample size, study continues to complete the enrollment per re-estimated sample size	A Promising zone: the conditional power is in between 40% to 80%, suggesting that the interim analysis result is promising, but the study has to have an increased sample size to have at least 80% power to reject the null hypothesis
CP > 0.8	No sample size re-estimate. Complete the study per current protocol.	A favorable zone: the conditional power is fairly high, suggesting that the interim result is as good or better than the expectation, the study has fairly high probability to reject the null hypothesis as is. This zone is defined to be CP > 80%.

To protect the data integrity, an independent statistician/programmer who is not involved with the study will be responsible to perform the analysis. A Data Monitoring Committee (DMC) will be formed to review the interim analysis results. All members of the DMC will not be involved with the conduct of the study. To perform the interim analysis, the independent statistician will receive the conspicuity score assessed by the central reviewers and the randomization code for each video/subject. It is worthy to point out that randomization is only pertained to the treatment of IC vs Saline but the dose of IC will **not** be revealed for interim analysis.

The DMC may choose to share with the study team the aggregated results/data (e.g., summary tables) but the individual subject data will not be shared with the study team. All documentations for the interim analysis, including but not limited to analysis data, associated programs, summary tables and/or listings, and DMC communications, will be securely stored away until the study database is locked.

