3.4. Test Hypothesis and *P* Value Justification

The study has a planned interim analysis to review the effect size assumption used to determine the sample size. To control for the overall alpha for the primary efficacy analysis, an alpha of 0.0001 will be used for the interim analysis, and alpha of 0.0499 will be used for the final analysis. The details of the interim analysis, including scope, method, and decision rules, will be described in the Data Monitoring Committee charter.

In the final analysis, there are two null hypotheses for the primary efficacy endpoint conspicuity.

1. there is no difference between the IC high dose and the normal saline

2. there is no difference between the IC low dose and the normal saline

Multiplicity due to the two null hypotheses will be controlled by Hochberg method. That is, to control family-wide Type I error to be less than or equal to 0.0499, the two p-values will be ordered from large to small. When both nominal p-values are less or equal to 0.0499, both null hypotheses will be rejected and one will conclude that both IC dose groups are statistically different from the saline group in the examined parameter. When the larger nominal p-value is greater than 0.0499 but the smaller p-value is less or equal to 0.025, the null hypothesis associated with the larger p-value is accepted and the null hypothesis associated with the smaller nominal p-value will be rejected. If the smaller nominal p-value is greater 0.025, the null hypothesis associated with this p-value is also accepted. The Overall Type I error control will apply to the primary endpoint conspicuity only.

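### Interim conditional power and the 80% target rest on a pooled IC-versus-saline comparison, but the final analysis tests each dose separately and the visible SAP does not say which outcome they stand for

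*SAP*

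**What the plan says.** **Interim (SAP Section 3.2).** Because dose is not unmasked, "the overall IC treatment effect will be analyzed using the proportional odds model", with terms for treatment (IC or saline) and ureter. The log odds ratio and its standard error give one Z. Equation 2 turns that Z into the probability of a significant final result at two-sided 0.05, with P = 0.5. The stated aim is modest: "The objective of this interim analysis is to confirm the observed treatment effect size on the conspicuity score from the test dataset".

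**Decision rule (Table 3).** The study stops if CP is below 0.20, continues unchanged from 0.20 to below 0.40, has its size re-estimated from 0.40 to 0.80, and continues unchanged above 0.80. The re-estimation row calls for an "increased sample size to have at least 80% power to reject the null hypothesis". That null hypothesis is singular and is not named.

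**Final analysis (Sections 3.4 and 5.1).** "In the final analysis, there are two null hypotheses for the primary efficacy endpoint conspicuity": High dose against saline and Low dose against saline. Both are rejected if both p-values are at most 0.0499. Otherwise a stricter level applies: "When the larger nominal p-value is greater than 0.0499 but the smaller p-value is less or equal to 0.025", only the null with the smaller p-value is rejected. Section 5.1 fits a separate model for each comparison, and its example dataset for the High-dose comparison holds High-dose subjects only. Neither Section 5.1 nor the table list in Section 8.1 shows a pooled IC-versus-saline test of the primary endpoint.

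**The concern.** Equation 2 gives the probability that a test on the same comparison will be significant at the end. Here the comparison pools both doses, and no final primary test does. Section 3.2 calls the interim model identical to Model 2. The terms do match, but Model 2 is fitted within one dose group, on about half the subjects.

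The pooled CP is therefore not, as computed, the probability of any Section 3.4 outcome. It could be read as the chance for a named dose, for at least one dose or for both, and these can differ widely. The reading matters because Table 3 can end the trial or set its final size on this number.

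**Working it through.** **Inputs.** From SAP Section 3.2: P = 0.5, two-sided 0.05, and 116 - 21 = 95 remaining subjects. Half of 95 is 47.5, which reproduces the stated 47-48. From Section 3.4: 0.0499 (critical value 1.961) and 0.025 (2.241). Assumed: 1:1 dose allocation, equal variances, each dose compared with its own subjects' saline, and continuation of the interim trend.

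**Step 1: pooled CP.** At P = 0.5, equation 2 is CP = Φ(2Z - 1.960/√0.5) = Φ(2Z - 2.772). Inverting it at Table 3's boundaries:
- CP 0.20: Z = (-0.842 + 2.772)/2 = 0.965
- CP 0.40: Z = (-0.253 + 2.772)/2 = 1.259
- CP 0.80: Z = (0.842 + 2.772)/2 = 1.807

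Using 0.0499 instead of 0.05 changes these CPs by less than 0.001.

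**Step 2: convert to the final tests, equal dose effects.** Each dose has half the subjects, so its Z is Z/√2. At pooled CP 0.80 this is 1.807/1.414 = 1.278.
- At 0.0499: a = Φ(2 × 1.278 - 1.961/√0.5) = 0.414
- At 0.025: b = Φ(2 × 1.278 - 2.241/√0.5) = 0.269
- Both rejected: a² = 0.171
- A given dose rejected: a² + b(1 - a) = 0.171 + 0.269 × 0.586 = 0.329
- At least one rejected: 2 × 0.329 - 0.171 = 0.487

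This treats the two *observed* dose Zs as identical. If only the *true* effects are equal, the observed split is random given the pooled Z: Z_H = (Z + e)/√2, Z_L = (Z - e)/√2, e ~ N(0,1), with drift Z/√2 per dose. Integrating over e gives the second figure in each cell.

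| Pooled CP | A given dose | At least one | Both |
|---|---|---|---|
| 0.20 | 0.04 / 0.07 | 0.07 / 0.14 | 0.01 / 0.005 |
| 0.40 | 0.095 / 0.14 | 0.16 / 0.26 | 0.03 / 0.02 |
| 0.80 | 0.33 / 0.35 | 0.49 / 0.58 | 0.17 / 0.13 |

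With 60:40 allocation, the 0.33 becomes 0.40 for the larger group and 0.25 for the smaller.

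**Step 3: unequal effects at pooled CP 0.80.** The probability of at least one rejection is about 0.75 with a 75/25 split, 0.80-0.83 with 80/20, and 0.95-0.97 if one dose carries everything.

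**Step 4: the error can reverse.** Let Z_High = 1.6 and Z_Low = -0.3. Pooled Z = (1.6 - 0.3)/√2 = 0.919 and pooled CP = Φ(1.838 - 2.772) = 0.18, in the stop zone. For High at 0.025, Φ(3.2 - 3.170) = 0.51. Low contributes almost nothing, so the probability of at least one rejection is 0.51.

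**Step 5: re-estimation.** The SAP gives no formula. I set P = 47.5/N in equation 2 and solve for pooled CP = 0.80. From pooled CP 0.40, 0.50, 0.60 and 0.70 this gives about 219, 178, 146 and 119 evaluable subjects, not counting the 21 treated earlier. With equal dose effects, those sizes leave a given dose at about 0.37-0.42 and at least one at about 0.54-0.63. From pooled CP 0.60, with identical observed dose Zs, reaching 0.80 would need about 224 (at least one), 324 (a given dose) or 408 (both), against 146.

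**Step 6: very large effect.** At pooled Z = 3.5, with identical observed dose Zs, the probabilities are 0.985 (a given dose), 0.999 (at least one) and 0.97 (both). No Table 3 decision changes.

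**The case against.** The pooled estimate is a deliberate choice. The primary objective names no dose and asks only whether IC "provides a visualization advantage compared to saline when used as an aid in the determination of ureteral patency". Masking dose protects the trial, and a pooled estimate suits an interim look meant to confirm an effect size. All of that stands. It justifies estimating a pooled effect, but not reading the result, unconverted, as the power of two dose-specific tests.

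The mapping may exist elsewhere. Section 3.4 refers interim methods and decision rules to the DMC charter, which is not supplied, and the sample-size rationale in Section 3.1 and Table 2 is redacted. This limits confidence about practical impact. It does not remove the mismatch in Section 3.2, which already states the model, formula, alpha and zones without a conversion.

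A vivid dye may also produce an effect so large that nothing turns on the point. That is fair, but Table 3 is written for the cases where it does not.

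A reader might infer that pooled CP always overstates the chance of success, or that a size re-estimated to pooled CP 0.80 can never give 80% for a final outcome. The documents do not support this, because they give no dose split. With an 80/20 split, re-estimation leaves at least one at 0.81-0.83, and with all the effect in one dose at 0.95-0.97. Nor does the mismatch show inflated type I error in the final tests.

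**Conclusion.** The point holds on the visible text and should be settled before the interim. The CP and the 80% target belong to a comparison that the final primary analysis does not test, and the SAP does not say which Section 3.4 outcome they represent. With pooled CP at 0.80, the chance of at least one rejection runs from about 0.49 (equal effects) to 0.97 (one dose only); the chance of both stays at 0.17 or below. The figures assume 1:1 allocation, equal variances, own-subject saline controls and a continuing trend. The re-estimated sizes also depend on a rule that the SAP does not give. What is affected is the interim decision and the power it is meant to secure. The validity of the final tests is not in question on this ground.

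**What to change.** In Section 3.2 and Table 3, name the Section 3.4 outcome to which CP and the 80% target refer: a given dose, at least one dose, or both. Compute CP and any re-estimated size as the probability of that outcome under the Hochberg rule with final alpha 0.0499.

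This can be done with dose masked. Assume equal true dose effects and 1:1 allocation, set the drift for each dose to Z_pooled/√2, and integrate over the unobserved interim split as in Step 2. If Z_pooled/√2 is simply entered for both doses, state that this assumes identical observed dose Zs; at the stop boundary it gives 0.07 rather than 0.14 for at least one. Report sensitivity to unequal splits. If the DMC charter already gives a mapping, bring it into the SAP.

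The cost is SAP and charter wording, a short calculation, and usually a less favourable stated CP and a larger re-estimated size. Unmasking dose to the independent statistician to obtain dose-specific CPs is optional and not needed for this fix. It is a design trade-off, and Section 3.2's permission for the DMC to pass aggregated results to the study team would then need restricting.
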